## 1.10 Biometrics concept of AGIL-CV

*Biometrics concept as an addition to AGIL-CV:*

Using stepwise regression analyses with forward and backward techniques, all partial correlations between the primary parameters and the other disease and patient characteristics are determined at baseline. The impact of disease and patient characteristics on the changes in each of the primary parameters is established by means of these regression analyses at Months 12, 24 and 60. In particular, the DAS28 response (defined as the critical difference [dcrit] of  $\leq -1.8$  points, constituting an improvement of 1.8 points in DAS28) or DAS28 nonresponse was used as a coded variable.

In addition, the observed difference between the DAS28 responders (patients with a dcrit of  $\leq -1.8$  at 5 of 7 visits) and the DAS28 nonresponders (dcrit  $> -1.8$ ) is tested using the general linear model. Missing data are replaced using the Last observation carried forward (LOCF) method.

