## 1.3 Research question

*Description of study aims AGIL-CV as a supplement to AGIL:*

The **primary research questions of AGIL-CV** are

- To determine baseline changes in Months 12, 24 and 60 after starting adalimumab treatment with regard to the following primary cardiovascular and metabolic parameters:
  - Lab chemistry blood parameters for glucose and lipid metabolism
  - Vital signs
  - Body measurements
- The comparison between DAS28 responders and DAS28 nonresponders in terms of the primary parameters "lab chemistry blood parameters for glucose and lipid metabolism" and "vital signs"
- Determination of the time point and frequency of cardiovascular events in the course of the entire documentation

The secondary **research question** addresses the investigation of the impact of the

---

personal data and familial medical history recorded at baseline on the previously specified cardiovascular and metabolic parameters. The Systematic Coronary Risk Evaluation (SCORE) risk model is applied to determine the individual risk and changes thereof over time.

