### **Examinations over the course of the study (Month 3, 6, 12, 24, 36, 48, 60) to determine cardiovascular risk factors**

Body measurements (except height)

Vital signs

Laboratory parameters

Tobacco use

Documentation of cardiovascular events

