### **1.9 Sample size estimation**

*Sample size estimation for AGIL-CV as a supplement to AGIL:*

The sample size estimation is based on published data concerning the blood pressure of RA patients (14):

Assuming an alpha and beta error of 5% each, the following minimum number of RA patients is required at the evaluation time points of Months 12, 24 and 60:

- N=128 patients are required in order to detect a mean systolic blood pressure difference of 10 mmHg (given a mean systolic blood pressure of 128 mmHg with a standard deviation of 18 mmHg).
- N=136 patients are required in order to detect a mean diastolic blood pressure difference of 5 mmHg (given a mean diastolic blood pressure of 74 mmHg with a standard deviation of 11 mmHg).

In documentations with adalimumab, premature discontinuation has been observed for approx. 50% of patients in the course of a 60-month documentation duration. If this rate is taken into account; an overall number of N=300 patients is sufficient to address the primary research questions given the above-named estimations.

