## 1.11 Time points of statistical analysis

*Analysis time point of AGIL-CV as a supplement to AGIL:*

Statistical analyses for the primary research questions are planned for Months 12, 24 and 60. For the secondary research questions, previous cardiovascular results are taken into account at these analysis time points.

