Course of work productivity and work ability, the course of health-related quality of life, and changes in functionality under long term treatment with adalimumab will be documented. The numbers of patients included in the NIS allow identifying and quantifying the impact of disease and patient characteristics on the therapeutic success.

7 Study Objectives

In this NIS, a long term documentation of treatment with adalimumab in RA patients over 60 months with 8 data collection points (visits) is planned. The documentation will be performed by the physician as well as by patient's self-assessment.

The primary objective is to explore the therapeutic success by interim analyses after 12 and 24 months of treatment as well as by the final analysis after 60 months of treatment. Improvements concerning the following target variables will be evaluated (with regard to the respective baseline value):

- the number of missed working days
- the self-assessed work ability (WPAI)
- the severity of clinical symptoms (number of tender and swollen joints, CRP and ESR, respectively; total score DAS28)
- Severity of functional impairment (HAQ)
- The health-related quality of life (EQ-5D)

At month 3, patient and disease characteristics will be evaluated with regard to their additional impact on changes in the number of affected joints (DAS28), in the HAQ, and in the WPAI. The impact on the number of missed working days will be evaluated at month 6.

The secondary objective is to document the therapeutic success by interim analyses at month 12 and 24 months as well as by the final analysis after 60 months. The therapeutic success will be evaluated by the following variables:

- The number of physician visits
- The number and duration of hospitalizations
- The number of days of impairment in non-occupational activities
- The duration of morning stiffness, pain, exhaustion/fatigue

- The reduction of number and dose of concomitant medication
- Patient's assessment of adalimumab therapy compared to previous therapies

Target parameters for safety evaluation of adalimumab are:

- The evaluation of safety and tolerability by the documentation and analysis of serious adverse events (SAEs) and adverse events (AEs).
- Evaluation of safety and tolerability for subgroups of patients with common frequent concomitant diseases, especially diabetes type II, cardiovascular, liver, and renal insufficiencies, and related concomitant medications.

8 Investigational Plan

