8.4 Study Duration

The duration of the whole NIS is estimated to be about 9 years.

Study start: March 2009

Recruiting phase: March 2009 – March 2012

Data completion: March 2017

Data analysis and final report: March 2017 – March 2018

For each individual patient, the NIS starts with the enrollment in the long term documentation at the beginning of the treatment with adalimumab and ends either after 5 years or with the termination of the adalimumab therapy.

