12.6 Times of Statistical Analyses

Interim analyses are planned after 3 and 5 years after the inclusion of the first patients, so that at month 12 and 24 sufficiently large groups of about 800 patients are available. The general analysis will be performed after closure of the follow-up of the last patient (8 years after starting the study).

13 Final Report and Publications

After the end of the NIS, an Integrated Final Report is generated in cooperation with the Principal Investigator, who also signs the report. The report includes a description of the objectives of the NIS, the employed methods, the results, as well as the conclusions. As the property of Abbott GmbH & Co. KG, the completed CRFs and the report are to be treated as confidential and may not be made accessible to unauthorized persons in any form (publication or presentation) without the explicit approval of Abbott GmbH & Co. KG. The results of this NIS may be published by Abbott GmbH & Co. KG or any of the participating investigators after approval by Abbott GmbH & Co. KG.

14 Literature

- (1) Lee, D.M., Weinblatt, M-E. (2001). Rheumatoid arthritis. Lancet; 358, 903-911.
- (2) Backman, C.L. (2004). Employment and work disability in rheumatoid arthritis. Current Opinion in Rheumatology; 16, 148-152.
- (3) Tony H.-P., Hein G., Richter C. et al. (2007). Adalimumab: Wirksamkeit und Sicherheit bei Patienten mit rheumatoide Arthritis in Deutschland: Zwischen- auswertung der Langzeitdokumentation HUM03-1 im Alltag der rheumatolo- gischen Praxis mit 4600 Patienten nach 24 Monaten Behandlung. Zeitschrift für Rheumatology, 60, Suppl. 1, S42.05.
- (4) Van der Cruyssen, B., Van Looy, S., Wyns, B. et.al. (2005). DAS28 best re- flects the physician's clinical judgment of response to infliximab therapy in rheumatoid patients: validation of the DAS28 score in patients under inflixi- mab treatment. Arthritis Research & Therapy; 7, R1063-R1071.
- (5) Van der Heijde, D.M.F.M., van 't Hof, M.A., van Riel, P.L.C.M. et al. (1990). Judging disease activity in clinical practice in rheumatoid arthritis: first step in the development of a disease activity score. Annals of the Rheumatic Dis- eases; 49, 916-920.

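### The AGIL-CV responder rule (5 of 7 visits) yields no responders on data up to Month 12 or 24, and at Month 60 it depends partly on length of follow-up

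*Protocol*

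**What the plan says.** **AGIL-CV amendment (Protocol).** Section 1.3 lists this among the primary research questions: "The comparison between DAS28 responders and DAS28 nonresponders in terms of the primary parameters", covering the laboratory parameters and vital signs. Section 1.11 states: "Statistical analyses for the primary research questions are planned for Months 12, 24 and 60". The sample size in 1.9 is likewise given as the number "required at the evaluation time points of Months 12, 24 and 60", and the same section expects about half of patients to discontinue within 60 months.

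Section 1.10 uses DAS28 response in two ways.
- Paragraph 1: stepwise regressions at Months 12, 24 and 60, with response coded as an improvement of 1.8 points and no visit count.
- Paragraph 2: a general linear model comparing responders with nonresponders. The responder rule has a visit count, "at 5 of 7 visits) and the DAS28 nonresponders". Nonresponders are given only as a change above -1.8, without a count. No month is named. A closing sentence says missing data are replaced by LOCF and does not say which variables this covers.

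The follow-up schedule in 1.7 is "Examinations over the course of the study (Month 3, 6, 12, 24, 36, 48, 60"), seven visits. Footnote 1 to Table 1 lets the Month 60 column hold an earlier last visit.

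**Parent AGIL plan (Combined protocol and SAP).** Section 7 evaluates the parent's objectives "by interim analyses after 12 and 24 months of treatment as well as by the final analysis after 60 months of treatment". Section 12.3 analyses observed cases. Section 12 leaves detail to a SAP, to be finalised before the database is opened for the first interim analysis.

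**The concern.** A rule that needs five responding visits cannot be met before a fifth visit exists. If the primary responder comparison is run on the data available at Month 12 or Month 24, it has no responder group.

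At Month 60 the rule can be computed, but with half the patients expected to stop early, the number of observed responses needed depends on how long a patient stayed and on an unstated choice about LOCF. Responder status would then partly measure persistence on adalimumab. A difference in lipids, glucose or blood pressure between the groups could not be read simply as a difference by disease control.

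**Working it through.** **Inputs.** Follow-up visits at Months 3, 6, 12, 24, 36, 48 and 60 (amendment 1.7; parent 8.5.2). At least 5 responses out of 7 (1.10). Analyses at Months 12, 24 and 60 (1.11). Discontinuation of 50% by Month 60 and N = 300 (1.9). The dropout shape is not given, so constant-hazard and linear loss are both shown.

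**The plan's 7.** The parent's 8 data collection points (section 7) minus baseline = 7. This reproduces.

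**Months 12 and 24.** Visits due by Month 12: 3, 6, 12, so at most 3 responses. By Month 24: one more, so at most 4. Both are below 5. Counting baseline does not help, because its change is 0.

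There are two ways to make the rule computable at these months:
- Fix status from all seven visits and apply it to Month 12 or 24 outcomes. This groups patients by DAS28 values recorded after the outcome.
- Carry the last value into visits not yet due. At Month 12 the rule then reduces to response at Month 12 alone (1 + 4 filled = 5). At Month 24 it reduces to response at Month 24 plus at least one earlier response (1 + 3 filled + 1 = 5). Those are different rules, and a visit not yet due is not missing data.

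**Month 60, LOCF applied to DAS28.** Fewest observed responses that reach 5 of 7, with the last observed visit a response and carried forward:

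| Last visit (month) | 3 | 6 | 12 | 24 | 36 | 48 | 60 |
|---|---|---|---|---|---|---|---|
| Slots filled | 6 | 5 | 4 | 3 | 2 | 1 | 0 |
| Observed responses needed | 1 | 1 | 1 | 2 | 3 | 4 | 5 |

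If a leaver's last visit is entered in the Month 60 column and the gap is filled from the last regular visit, the needed counts are 1, 1, 2, 3, 4, 5 for a last regular visit at Month 3, 6, 12, 24, 36, 48. The dependence remains.

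**Month 60, LOCF not applied to DAS28.** Fewer than five recorded DAS28 visits rules a patient out.
- Regular visits only (lost before Month 36): constant hazard 1 - 0.5^(36/60) = 0.340, about 102 of 300; linear 0.5 x 36/60 = 0.300, or 90 of 300.
- With an early last visit recorded as a fifth assessment (lost before Month 24): 1 - 0.5^(24/60) = 0.242, about 73; linear 0.5 x 24/60 = 0.200, or 60.

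The range is about 20-34%. DAS28 missed at attended visits would add to it: the parent's 8.5.2 documents data only if assessed in routine care.

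**Would counting observed visits among patients with five or more be enough?** Take an assumed, independent per-visit response probability of 0.6. The chance of at least 5 observed responses is:
- 5 visits: 0.6^5 = 0.08
- 6 visits: 6 x 0.6^5 x 0.4 + 0.6^6 = 0.23
- 7 visits: 21 x 0.6^5 x 0.4^2 + 7 x 0.6^6 x 0.4 + 0.6^7 = 0.42

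Under LOCF the same chances are 0.49, 0.44 and 0.42. Observed counting across unequal follow-up is therefore steeper in follow-up than LOCF for these patients, and is not a remedy. The 0.6 is illustrative only.

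**The case against.** **One classification over the whole follow-up was meant.** The general linear model sentence names no month, and in 1.3 only the item on baseline changes names Months 12, 24 and 60. A 5-of-7 rule reads naturally as a whole-study label, and 1.11 does not say whether its months are outcome time points or data cut-offs. This stands in part. A reader might infer that the responder group is simply empty at two of the three analyses. The documents do not support that without the condition that only data up to the month are used. But the plan never states the whole-study reading, 1.11 covers all primary questions without exception, and that reading groups Month 12 and 24 outcomes by later DAS28.

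**Response is already analysed at these months.** True: the paragraph 1 regressions use DAS28 response without a visit count. A reader might infer that AGIL-CV has no workable response analysis at Months 12 and 24; that would be wrong. The harm is limited to the general linear model comparison.

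**The calendar settles it.** The parent plan says "Interim analyses are planned after 3 and 5 years after the inclusion of the first patients" and "Recruiting phase: March 2009 – March 2012", which invites a calculation of how many patients would have five visits due at each interim. The amendment gives no calendar dates and takes its sample size inputs from a paper dated February 2011, so its patients may have joined late in that window. The parent timetable suggests separate looks at Months 12 and 24 but supports no percentage for AGIL-CV.

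**The SAP will handle it.** Section 12.3 does leave minimum documentation to the SAP. But 5 of 7 is a stated rule, so the SAP would have to replace it. The exploratory status in 12.4 concerns multiplicity and does not supply a responder group.

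**Nonresponders are obviously the complement.** Plausible, and one sentence would settle it.

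**Conclusion.** The point holds in this form. The stated rule gives no responders on data up to Month 12 or Month 24, two of the three months set for the primary questions. That is a count from the schedule and needs no assumption beyond using only data up to the month. The ways around it are unstated, and they either use later data or change the rule.

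At Month 60, responder status depends partly on length of follow-up whichever way LOCF is read. With LOCF on DAS28, one to five observed responses are needed according to the last visit. Without it, about 20-34% of patients cannot qualify, assuming 50% discontinuation, one of the two dropout shapes, and one of the two readings of footnote 1.

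Two stronger readings are tempting and not supported. One is that nobody last seen before Month 36 could ever be a responder: footnote 1 allows a recorded last visit to be the fifth. The other is that the comparison is biased by a known amount or in a known direction: that depends on response rates the documents do not give and on the unstated scope of LOCF.

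**What to change.** In the amendment, or in the SAP before the first interim analysis:

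1. For the general linear model comparison at Months 12, 24 and 60, classify by the 1.8-point criterion of 1.10 paragraph 1, applied to the DAS28 change from baseline observed at that month. Nonresponders are all other patients with an observed DAS28 at that month.
2. Do not use LOCF to assign responder status. Report how many patients cannot be classified at each month.
3. Keep the visit-count rule, worded as at least 5 of 7, only as a supplementary sustained-response comparison at Month 60 among patients with all seven DAS28 assessments, so that everyone faces the same bar. State that it describes completers.
4. State whether LOCF still applies to the outcomes.

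The cost is a few sentences and no new data. There are three downsides. A patient's status can differ between months. The sustained-response comparison covers only about half the patients (about 150 of 300 at 50% discontinuation) or fewer. Selection by persistence remains at Month 60 and should be stated with the results.

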**Table 1 Physician's overview – collection of cardiovascular and metabolic risk factors**

	Month							
	0	3	6	12	24	36	48	60 
Body measurements (weight, height, waist and hip circumference) 	X	X	X	X	X	X	X	X
Familial medical history (diabetes, obesity, premature cardiovascular disease)	X							
Tobacco use	X	X	X	X	X	X	X	X
Alcohol consumption	X	X	X	X	X	X	X	X
Vital signs 	X	X	X	X	X	X	X	X
Documentation of cardiovascular events (myocardial infarction, stroke)	X	X	X	X	X	X	X	X
Laboratory parameters (fasted) 	X	X	X	X	X	X	X	X

 Month 60 or last visit

 Height is only determined at Month 0.

 Data are incorporated into the SCORE risk model.

 Glucose (serum or plasma), lipid profile (HDL cholesterol, LDL cholesterol, total cholesterol, triglycerides, CRP)

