12.3 Missing Values

Missing observations will be documented as missing values. Instructions for the minimum documentation required for a patient to be evaluable will be established in the SAP.

All data will be analyzed on the basis of “observed cases”. For the statistical analysis of data concerning the course of disease, the health-related economic parameters and

the health-related quality of life (if related to changes from baseline values), an additional approach will be followed considering only patients with complete data at all visits.

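### LOCF in Section 1.10 conflicts with the observed-case rule in Section 12.3 and would make about half of the Month 60 values earlier on-treatment readings

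*Protocol*

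**What the plan says.** - **Protocol, Section 1.10.** "Missing data are replaced using the Last observation carried forward (LOCF) method". The sentence closes the paragraph on the general linear model comparing DAS28 responders with nonresponders. It names no variables, sets no limit on the visits filled and plans no sensitivity analysis. For this comparison a responder is a patient whose DAS28 has fallen by at least 1.8 points at 5 of 7 visits. The section introduces itself as "Biometrics concept as an addition to AGIL-CV" and does not mention Section 12.3.
- **Combined protocol and SAP, Section 12.3.** "All data will be analyzed on the basis of" observed cases. For changes from baseline, "an additional approach will be followed considering only patients with complete data at all visits". Carrying values forward is not part of this section.
- **Combined protocol and SAP, Section 8.4.** A patient's documentation "ends either after 5 years or with the termination of the adalimumab therapy".
- **Protocol, Section 1.9.** "premature discontinuation has been observed for approx. 50% of patients in the course of a 60-month documentation duration". The section requires 128 patients (systolic) and 136 patients (diastolic) at Months 12, 24 and 60, and arrives at N=300.
- **Protocol, Table 1.** The footnote to the last column reads "Month 60 or last visit".
- **Protocol, Section 1.3.** Change from baseline at Months 12, 24 and 60 is a primary question. So is the responder comparison, for laboratory values and vital signs.

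**The concern.** Two missing-data rules apply to the same patients, and an analyst cannot follow both. DAS28 would be analysed as observed in AGIL and might be carried forward in AGIL-CV.

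The rule in Section 1.10 meets a design in which visits after stopping are missing by construction. A blood pressure, lipid or glucose value from the last on-treatment visit would be analysed as the value at Month 12, 24 or 60. Any later drift in these parameters would be pulled towards the early change, and the standard errors would treat carried values as if they had been measured at that time.

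If DAS28 is carried as well, the grouping variable is affected along with the outcome, because a short good start can be scored as a sustained response.

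**Working it through.** **1. The plan's own figure.** Section 1.9 allows for 50% discontinuation: 128/(1 − 0.5) = 256 and 136/(1 − 0.5) = 272, both below 300. Conversely, 300 × (1 − 0.5) = 150 patients remain at Month 60, above 136. So N=300 was set to leave enough patients still under documentation, with no imputation. (The 136 is used here only as the plan's own benchmark. It does not follow from the stated SD of 11, difference of 5 and errors of 5% each: two equal groups, two-sided, need 2 × (1.960 + 1.645)² × (11/5)² ≈ 126 per group, 252 in total; a one-sample calculation with SD of change 11 needs 63. That is a separate matter.)

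**2. Share carried at Month 60.** Of 300 patients, 300 × 0.5 = 150 have stopped. Under LOCF about 300 are analysed, of whom about 150 contribute an earlier reading. This follows from Sections 1.9 and 8.4 alone.

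**3. Earlier time points.** The documents do not say when patients stop. I assume four curves, each reaching 50% at Month 60: constant rate, 1 − 0.5^(t/60); linear, 0.5(t/60); front-loaded, 0.5(t/60)^0.5; back-loaded, 0.5(t/60)².

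| Month | Stopped, constant rate (of 300) | Range over the four curves (of 300) |
|---|---|---|
| 12 | 13% (39) | 2–22% (6–67) |
| 24 | 24% (73) | 8–32% (24–95) |
| 36 | 34% (102) | 18–39% (54–116) |
| 60 | 50% (150) | 50% (150) |

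**4. Apparent precision.** For a mean change with equal spread, the standard error varies as 1/√n. Treating 300 values as measured instead of 150 multiplies it by √(150/300) = 0.71.

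**5. The 5-of-7 rule if DAS28 is filled.** The seven follow-up visits are Months 3, 6, 12, 24, 36, 48 and 60. With k observed visits and r observed responses, the LOCF count is r + (7 − k) if the last observed visit is a response, and r if it is not.

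| Last visit (a response) | k | Count if it is the only response | Fewest observed responses to reach 5 |
|---|---|---|---|
| Month 3 | 1 | 1 + 6 = 7 | 1 |
| Month 6 | 2 | 1 + 5 = 6 | 1 |
| Month 12 | 3 | 1 + 4 = 5 | 1 |
| Month 24 | 4 | 1 + 3 = 4 | 2 |
| Month 36 | 5 | 1 + 2 = 3 | 3 |
| Month 48 | 6 | 1 + 1 = 2 | 4 |
| Month 60 | 7 | 1 | 5 |

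The added term is never negative, so compared with counting five observed responses, LOCF can only turn nonresponders into responders. Conversely, Month 36 is the fifth follow-up visit, so without LOCF nobody who stops before it can reach five.

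**6. How often this would happen.** This needs inputs that the documents lack. Enumerating all visit patterns with independent per-visit response of 30%, 50% or 70%, the four curves above and stopping unrelated to response, 19 to 81 of 300 patients (about 6% to 27%) change class. The link between stopping and response matters. In simulations with response of 40–60% and within-patient correlation of 0.3–0.6, the share of LOCF responders with fewer than five observed responses is 40–54% if stopping is unrelated to response. It is 26–34% if nonresponse triples the stopping rate and 19–24% if it multiplies it by five.

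**The case against.** The best defence is one of scope and status. The LOCF sentence sits in the paragraph on the responder comparison and may govern only that. Table 1's "Month 60 or last visit" suggests that a last on-treatment value was intended all along. The study is non-interventional; Sections 12.4 and 12.5 call its analyses exploratory and mainly descriptive, and Sections 12 and 12.3 leave detail to a later SAP.

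Part of this stands. The reach of the sentence is unclear, so a reader who infers that every missing value in AGIL-CV is filled goes beyond the text. But the responder comparison is itself a primary question, so even the narrow reading matters. The footnote shows an unstated target, not a justification: a last on-treatment value is not a Month 60 value. A later SAP cannot follow both stated rules.

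Four stronger readings are tempting and are not supported:

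- *The carried values are invented.* They are real measurements assigned to a later time.
- *LOCF contradicts Section 1.9.* Nothing there forbids imputation. The planning basis differs, but there is no textual contradiction.
- *A patient who responds at Months 3, 6, 12 and 24, fails at Month 36 and stops is made a nonresponder by LOCF.* That patient scores 4 of 7 with or without it.
- *Many responder labels would be wrong.* The documents give no response rates. Having fewer than five observed responses is also a poor measure of error, because anyone who stops before Month 36 must fall short, however well they responded.

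**Conclusion.** The point holds in this form. Sections 1.10 and 12.3 give incompatible missing-data rules, and neither yields to the other. Followed as written, Section 1.10 makes about 150 of 300 Month 60 values earlier on-treatment readings, with estimates pulled towards early change and standard errors that are too small. This affects at least the primary responder comparison, and also the change-from-baseline and regression analyses if the sentence covers them.

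The figure of 150 rests on the plan's approximate 50% and on documentation ending at stopping. The counts at earlier months rest on assumed stopping curves. That one response at an early last visit can satisfy the 5-of-7 rule is certain if DAS28 is filled; how many patients this affects cannot be settled from the documents.

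**What to change.** Amend Section 1.10 and carry the change into the SAP:

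1. Replace the LOCF sentence with a likelihood-based repeated-measures model on observed visits, with terms for baseline value, visit, responder status and visit by status. Report the number observed at each visit. State that this rests on missingness being explained by the observed data.
2. Say how this relates to the observed-case and complete-data analyses in Section 12.3, and which AGIL-CV analyses it covers.
3. Analyse a last visit before Month 60 at its actual time, not in the Month 60 column.
4. Classify responders from observed visits only, with a stated count for early stoppers, for example response at no fewer than 5/7 of observed visits. Merely ceasing to carry DAS28 forward, with five responses still required, would make everyone who stops before Month 36 a nonresponder (about 102 of 300 at a constant rate) and confound response with persistence on treatment.
5. If LOCF is kept, make it a sensitivity analysis labelled as the last on-treatment value.

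No new data or patients are needed. The cost is wider intervals and a smaller stated n at Month 60 (about 150, above the plan's minimum of 136), and responder status that rests on fewer visits for early stoppers.
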